Nature contact has been linked to psychological and physiological well-being in human beings (Bratman et al., 2019). As outlined by Frumkin et al. (2017), these benefits include stress reduction (assessed via decreased heart rate, blood pressure, cortisol levels, and self-report measures), decreased anxiety, negative affect, and depressive symptoms, and increased positive affect, prosocial behavior, and attentional capacity (Beil & Hanes, 2013; Berman et al., 2008; Bratman et al., 2015; Duncan et al., 2014; Ewert & Chang, 2018; Hong et al., 2018; Hunter et al., 2019; Jiang et al., 2014; Kaźmierczak, 2013; McAllister et al., 2017; Piff et al., 2015; Putra et al., 2020; Ward Thompson et al., 2016; Zhao et al., 2022). Additionally, nature contact has been associated with improved sleep, reduced mortality, and reduced risk of Type II diabetes (Astell-Burt et al., 2014; Astell-Burt & Feng, 2020; Bodicoat et al., 2014; Gascon et al., 2016; James et al., 2016; Johnson et al., 2018; Shin et al., 2020). Despite these demonstrated associations, the causal mechanisms that may be responsible for these effects are less well known. One possible pathway is reduction of stress and associated anti-inflammatory psychoneuroimmunological processes (Hartig et al., 2014; Kuo, 2015; Ulrich et al., 1991).

Shinrin-yoku, also known as "forest bathing", is a specific set of human-nature interactions that have been shown to improve mood, reduce anxiety and depressive symptoms, and have beneficial effects on HRV, blood pressure, HR, stress hormone levels, and inflammatory biomarkers (De Brito et al., 2020; Furuyashiki et al., 2019; Horiuchi et al., 2014; D.-S. Kim et al., 2015, 2015; Kobayashi et al., 2017, 2018; Lanki et al., 2017; J. Lee et al., 2015; Li et al., 2007, 2008; Mao, Cao, et al., 2012; Mao, Lan, et al., 2012; Ochiai et al., 2015; Oomen-Welke et al., 2022; B. J. Park et al., 2009; B.-J. Park et al., 2007; Song et al., 2015, 2017; Stigsdotter et al., 2017; Tsunetsugu et al., 2013; Yu et al., 2017). However, some studies have not observed significant changes or reported contrary observations when comparing outcomes following forest exposure to earlier baseline measurements or outcomes following control exposure, including no significant difference or a difference against the hypothesized direction in mood, stress hormone levels, blood pressure, and HRV (De Brito et al., 2020; Furuyashiki et al., 2019; Gidlow et al.,

2016, 2016; Horiuchi et al., 2014; Kavanaugh et al., 2022; Y. Kim et al., 2022; Lanki et al., 2017; Mao, Cao, et al., 2012; Oomen-Welke et al., 2022; Stigsdotter et al., 2017; Yu et al., 2017).

One possible pathway for the psychophysiological benefits of forest bathing is through exposures to terpene compounds that contribute to the smell of the forest (Li et al., 2008). Terpenes are types of biogenic volatile organic compounds (BVOCs). Over 55,000 different chemically structured terpenes have been identified, all generally with a $(C_5H_8)_n$ chemical formula, and classified by differences in linked isoprene units (Kanwal et al., 2022). Emitted by plants, terpenes aid in plant reproduction, defense, interand intraspecific interactions, and abiotic stress response (Dudareva et al., 2006).

In animal and *in vitro* experiments, terpenes have demonstrated anti-inflammatory, antitumorigenic, and neuroprotective action (Cho et al., 2017). As summarized by De Cássia Da Silveira E Sá et al. (2013) and Eddin et al. (2021), rats, mice, and guinea-pigs exposed to terpenes displayed anxiolytic and anti-inflammatory responses via reduced plasma corticosterone levels, reduced inflammation in colonic tissue, and a reduction in bronchial resistance, paw edema, and leukocyte, neutrophil, IL-1 β , TNF- α , and IL-6 levels (Bastos et al., 2011; De Almeida et al., 2017; Nascimento et al., 2009; Saiyudthong & Marsden, 2011; Santos, 2004; Zhang et al., 2018). Additionally, terpene exposure was shown to increase white blood cell count, IL-2, IL-10, T cell, and lymphocyte levels, and antibody cell production in rats and mice (Badr et al., 2011; Raphael & Kuttan, 2003; Trinh et al., 2011).

In human monocytes, terpenes can inhibit production of inflammatory cytokines, leukotrienes, and associated metabolites, including TNF- α , IL-1 β , II-4, II-5, IL-6, IL-8, and leukotriene B4 (LTB4; De Cássia Da Silveira E Sá et al., 2013; Hart et al., 2000; Juergens et al., 1998, 2004). Additionally, terpene or essential oil exposure has been associated with anti-inflammatory effects in asthma patients, reduced anxiety and depressive symptoms, reduced stress, increased positive affect, and improved cognitive function and sleep (Chen et al., 2022; Fung et al., 2021; Goes et al., 2012; Juergens et al., 2003; Kerr et al., 2021; Koyama & Heinbockel, 2020; M. Lee et al., 2017; Moss & Oliver, 2012; Woo et al., 2023). These anti-inflammatory, anti-cancer, antioxidative, and neuroprotective properties of forest-derived terpenes may be mediated by signal transduction (i.e., a relay of signals within a cell) and changes in the production of transcription factor proteins that regulate gene transcription (i.e., NF-κB; Cui et al., 2022; D.-S. Kim et al., 2015; T. Kim et al., 2020; Latchman, 1993; Nair et al., 2019; Rufino et al., 2014).

Aoshima and Hamamoto (1999) proposed several pathways through which fragrant compounds might affect the brain: stimulation of the olfactory system and resulting psychological effects, absorption into the blood via the lungs by respiration, skin application, and gastrointestinal exposure via food. Similar pathways for essential oil inhalation were summarized by Fung et al. (2021). With respect to the olfactory system: essential oil molecules can bind to chemoreceptors in the nasal cavity and activate neural signaling, resulting in psychological changes (Cui et al., 2022; Faturi et al., 2010; Kagawa et al., 2003). Additionally, essential oil molecules may move through the olfactory system neuronal network via extracellular delivery or mucosa, arriving in the brain in a similar way to nasally delivered medications (Chioca et al., 2013; Cui et al., 2022; Fung et al., 2021; Hanson & Frey, 2008). From there, they may interact with transient receptor potential channels (TRP), gamma-aminobutyric acid, serotonin, and dopamine receptors (Hanson & Frey, 2008). Finally, essential oil molecules may also be transported via lung alveoli and blood to interact directly with the CNS (Chioca et al., 2013; Faturi et al., 2010; Fung et al., 2021; Kagawa et al., 2003).

In this study, participants were exposed to terpenes via inhalation of ambient forest air. Most inhaled air enters through the nose, and although human beings switch to oral breathing during exercise, approximately 30-35% of air is still inhaled via the nose in those cases as well (Koenig, 2000). Sense of smell, or olfaction, refers to the sensory process through which the olfactory system and brain interpret odors from the surrounding environment (Doty, 2001). The olfactory epithelium that lines the interior of the nose consists of olfactory receptor neurons (ORNs) that bind with odorants (Purves & Williams, 2001). ORN axons project sensory information to neurons in the olfactory bulb, which then project to the pyriform cortex in the temporal lobe, as well as the hypothalamus and the amygdala.

Olfaction and affective responses are linked in experimental studies, in part because odors can directly elicit individual affective responses following exposure (Kontaris et al., 2020; Retiveau et al., 2004; Seubert et al., 2008). Some odors may impair working memory, while others reduce anger and

depressive symptoms, and improve mood (Komori et al., 1995; Martin & Chaudry, 2014; Retiveau et al., 2004; Schiffman et al., 1995). As outlined by Durrant et al. (2016), the olfactory bulb might also be the site of an early innate immune response, as experimental studies of mice found olfactory bulb expression of proinflammatory cytokines, including TNF- α , TNFR1, IL-1 β , IL-6, and I κ B kinase (Aniszewska et al., 2015; Leyva-Grado et al., 2009; Mori et al., 2005). In-vitro experiments have also shown that olfactory ensheathing cells (OECs) may activate NF- κ B transcription factors, express Toll-like receptors (TLR) 2 and 4, and express inducible nitric oxide synthase (iNOS) mRNA and enzymes in response to bacteria and pathogen incubation (Harris et al., 2009; Vincent et al., 2007).

Here, we aim to fill a critical gap in knowledge by examining whether terpenes play a role in the health effects of nature contact in a real-world forest environment by assessing whether terpene inhalation, with a focus on the olfactory pathway, impacts stress reduction and affective outcomes using a randomized double-blind crossover trial design. The primary outcome was the HF component of HRV, a measure of parasympathetic nervous system (PNS) activity, or relaxation (add some citations to back up this claim). Secondary outcomes included measures of skin conductance levels (SCL), blood pressure, and HR (i.e., measures of sympathetic nervous system activity, or stress), self-reported stress and affect, and levels of inflammatory cytokines in serum. Terpene concentrations in serum were measured to assess the degree of association of absorbed dose with study outcomes. We predicted that exposure to forest terpenes would be associated with greater increases in HF HRV and positive affect, and greater decreases in SCL, blood pressure, HR, self-reported stress, negative affect, and levels of inflammatory cytokines in serum compared to the condition with no forest terpenes exposure. Additionally, we predicted that study outcomes would be associated with absorbed dose of forest terpenes.

To our knowledge, no study has been conducted that concurrently investigated real-world ambient terpene exposure in a forest, absorption of these terpenes, and impacts of experimental vs. control conditions of these terpene exposures on psychophysiological and immunological effects in human beings. Therefore, this study aims to further scientific understanding of the role that forest terpene inhalation exposures play in the multisensory pathways that link human well-being and forest exposure.

5. References

Aoshima, H., & Hamamoto, K. (1999). Potentiation of GABA Receptors Expressed in Xenopus Oocytes by Perfume and Phytoncid. *Bioscience, Biotechnology, and Biochemistry*, *63*(4), 743–748. https://doi.org/10.1271/bbb.63.743

### 1. Exclusion criteria:

Potential participants were screened via a phone call and excluded if they were pregnant, smoking, and/or had a current or prior diagnosis of neurologic, hypertensive, psychiatric, respiratory disorder, or anosmia/hyposmia. Participants were also excluded if they were prescribed a short list of prescription medications known to influence terpene metabolic pathways and short-term inflammatory biomarkers including beta-blockers, antibiotics, statins, hypertension medications, steroid medications, and diabetes control medications. Eligible participants were asked to avoid certain foods, beverages, cleaning products, and supplements that contain terpene compounds in the 24 hours leading up to their forest sitting experience.

Additionally, the clinically validated University of Pennsylvania Smell Identification Test (UPSIT) (Sensonics International, Haddon Heights, NJ) was administered to determine whether participants had anosmia/hyposmia. The UPSIT is a 40-item, self-administered "scratch-and-sniff" test that uses microencapsulated odorants that are released by scratching designated spaces on a paper test booklet. Summed scores were used to evaluate olfactory function and identify/exclude participants with undiagnosed smell loss or total anosmia (summed UPSIT score  $\leq 18$ ).

# 2. Specific Aims

2. 1. Aim 1. Assess whether VOC inhalation regulates stress reduction and affective outcomes of the terpenes-on vs. terpenes-off sessions.

Primary physiological outcome: increases in the HF (ms) component of HRV.

Secondary outcomes: decreases in blood pressure, heart rate, self-reported stress, negative affect, and levels of inflammatory cytokines (IL-6, TNF-alpha, CRP) and cortisol in serum, and increases in positive affect, measured via mobile physiology equipment and blood using standard clinical methods.

Hypothesis: VOC inhalation will regulate increases in the HF (ms) component of HRV and decreases in blood pressure, heart rate, self-reported stress, and levels of inflammatory cytokines in serum as secondary outcomes.

2. 2. Aim 1a. Assess the degree of association of absorbed dose of seven forest-derived VOCs in serum (i.e.,  $\alpha$ - pinene,  $\beta$ -pinene,  $\beta$ -myrcene,  $\Delta$  3- carene, limonene,  $\beta$ - carophyllene,  $\alpha$ -humulene) with these outcomes.

Hypothesis: Absorbed dose of seven forest-derived VOCs in serum will be associated with stress reduction and affective outcomes.

## 3. Statistical Analysis

# 3.1 Exploratory Analysis

Histograms and descriptive statistics of the study data were plotted/calculated for the manuscript. Histograms and boxplots of UPSIT scores, time in nature, time in nature setting, frequency in nature, PSS scores, PROMIS (4-item Anxiety Scale) scores, and PANAS scores were plotted. Spaghetti plots of HF HRV, SCL, SF-PANAS scores, systolic and diastolic blood pressure, heart rate, and self-reported stress were plotted. Boxplots of inflammatory biomarkers were plotted.

Primary outcome: High Frequency Heart Rate Variability

- Check for missing or out-of-range values
- We applied a natural logarithmic transformation to 5-minute averages of HF HRV (hereafter called ln-HF HRV), following established precedent in prior literature (Shaffer and Ginsberg, 2017).

Secondary outcomes: Blood pressure, heart rate, self-reported stress, SF-PANAS positive affect, SF-PANAS negative affect, and levels of inflammatory cytokines (IL-6, TNF-alpha, CRP) and cortisol in serum, measured via mobile physiology equipment and blood using standard clinical methods.

- Check for missing or out-of-range values
- Explore imputation approaches for missing PANAS items
- One CRP observation was right-censored. The observation was set to the limit of quantitation (35.98 mg/L) and CRP observations were log transformed.
- As the machine values for left-censored IL-6 observations are closest to the true values, machine values will be used for censored observations for primary analysis.

### 3.2 Primary Analysis: Linear Mixed Effect Model

We will calculate the main effect of the filter on the difference between baseline measurements and time point 2 (T2) for ln-HF HRV, skin conductance levels, self-reported stress, positive and negative affect levels (SF-PANAS) and timepoint 4 (T4) for systolic blood pressure, diastolic blood pressure, heart rate, inflammatory biomarkers, and cortisol using a mixed effect model. Systolic blood pressure, diastolic blood pressure, heart rate, inflammatory biomarkers and cortisol data were collected at T4, but not T2. As the machine values for left-censored IL-6 observations are closest to the true values, machine values will be used for censored observations for the primary analysis. Sensitivity analyses will be performed for the IL-6 analysis by comparing model output using machine values to model output using limit of detection and zero and a logistic regression using a detect/non-detect variable. If using a different approach for imputing IL-6 changes the results substantially, then our result is not easily interpretable. Participants who completed only one session will also be included in analysis. Analyses will be conducted in R (version 4.3.1; R Core Team, 2023) using the lme4 R package (Bates et al., 2015). We will present the main effect results and associated statistics, including effect sizes and confidence intervals.

For ln-HF HRV, skin conductance levels, self-reported stress, positive and negative affect levels (SF-PANAS):

$$Y_{is} = \beta_0 + \beta_1 baseline_{is} + \beta_2 filter_{is} + \alpha_i + \varepsilon_{is}$$

Where:

•  $Y_{is}$  is the observed average outcome for individual *i* at T2, and session *s* where *s* is session 1 or session 2

- $\beta_0$  is the average  $Y_{is}$  for the study population at T2 when they were assigned the A filter, adjusted for baseline.
- $\beta_I$  is the estimated difference in  $Y_{is}$  at T2 between two groups differing in baseline by 1 unit.
- $\beta_2$  is our primary coefficient of interest and is the estimated difference in  $Y_{is}$  between the A filter and the B filter at T2, adjusted for baseline.
- $\alpha_i$  is the random intercept for subjects to account for repeated measures within individuals
- $\varepsilon_{is}$  is the observation-specific error

For systolic blood pressure, diastolic blood pressure, heart rate, inflammatory biomarkers, and cortisol:

- $Y_{is}$  is the observed outcome for individual *i*, at time point *t* where *t* is T4, and session *s* where *s* is session 1 or session 2
- $\beta_0$  is the average  $Y_{is}$  for the study population at T4 when they were assigned the A filter, adjusted for baseline.
- $\beta_1$  is the estimated difference in  $Y_{is}$  at T4 between two groups differing in baseline by 1 unit.
- $\beta_2$  is the average difference in  $Y_{is}$  between the A filter and the B filter, adjusted for baseline.
- $\alpha_i$  is the random intercept for subjects to account for repeated measures within individuals
- $\varepsilon_{is}$  is the observation-specific error

For positive and negative affect levels (SF-PANAS):

$$Y_{is} = \beta_0 + \beta_1 baseline_{is} + \beta_2 filter_{is} + \beta_3 missingscale item_{is} + \alpha_i + \varepsilon_{is}$$

Where:

- $Y_{is}$  is the observed average outcome for individual *i* at T2, and session *s* where *s* is session 1 or session 2
- $\beta_0$  is the average  $Y_{is}$  for the study population at T2 when they were assigned the A filter, adjusted for baseline and missing scale items.
- $\beta_1$  is the estimated difference in  $Y_{is}$  at T2 between two groups differing in baseline by 1 unit.
- $\beta_2$  is our primary coefficient of interest and is the estimated difference in  $Y_{is}$  between the A filter and the B filter at T2, adjusted for baseline and missing scale items.
- $\beta_3$  is the estimated difference in  $Y_{is}$  between two groups differing in missing affect scale items by 1 item, adjusted for baseline.
- $\alpha_i$  is the random intercept for subjects to account for repeated measures within individuals
- $\varepsilon_{is}$  is the observation-specific error

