Additionally, the clinically validated University of Pennsylvania Smell Identification Test (UPSIT) (Sensonics International, Haddon Heights, NJ) was administered to determine whether participants had anosmia/hyposmia. The UPSIT is a 40-item, self-administered "scratch-and-sniff" test that uses microencapsulated odorants that are released by scratching designated spaces on a paper test booklet. Summed scores were used to evaluate olfactory function and identify/exclude participants with undiagnosed smell loss or total anosmia (summed UPSIT score ≤ 18).

Following enrollment, participants were randomly assigned to a sequence of two sessions using a computer-randomized order created by an investigator who was not a member of the field team. To control participants inhalation exposures to terpenes in the forest air, participants wore a powered air-purifying respirators (PAPRs; 3M[™] Versaflo[™] Powered Air Purifying Respirator, TR-800-PSK/94248; 3M, St. Paul, MN). In one session, the PAPR mask was fitted with a particle-only filter (3M[™] Versaflo[™] High-Efficiency Filter, TR-6710N-5) to allow for the inhalation of forest terpenes ("terpenes-on"). In the other session, the mask was fitted with a charcoal filter (3M[™] Versaflo[™] Organic Vapor/HEPA Cartridge, TR-6510N) that removed particles, terpenes, and other BVOCs from the breathing zone ("terpenes-off"). Equipment labels were covered and filters were labeled "A" (later revealed to be "terpenes-off") to blind the study field team and participants to treatment assignment. A washout period of at least eight days between sessions was included to reduce carryover effects (Sibbald & Roberts, 1998).

Forest-sitting sessions took place at the UW Charles L. Pack Experimental Forest located near Eatonville, Washington ("Pack Forest") during June to September 2022 and 2023 to avoid rain, snow, and cold weather. The sessions were 60 minutes each and took place between 10:00 AM and 4:00 PM in a stand of old- and second-growth Douglas Fir, Western Red Cedar, and other conifers accessible by a 10-minute drive on an unpaved single-lane road from the Pack Forest Conference Center. Participants were seated in a comfortable chair, but the session was otherwise unscripted.

3. Methods

We enrolled 43 adult participants between July 12, 2022, and September 21, 2023. Our target sample size of 40 participants was based on the estimated numbers needed to detect minimum differences in the study

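### The IL-6 sensitivity rule judges interpretability against comparators that are expected to differ from a correct result, and leaves a substantial change undefined

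*SAP*

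**What the plan says.** IL-6 is one of the secondary outcomes, listed in SAP section 3.1 among "levels of inflammatory cytokines (IL-6, TNF-alpha, CRP) and cortisol in serum". Some values lie below the assay LOD. For these the SAP takes the instrument's own reading, on the ground that it lies nearest the truth: "machine values will be used for censored observations for the primary analysis" (section 3.2, repeated in 3.1). The model is a linear mixed model at T4 with baseline, filter and a random intercept per person.

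Section 3.2 then compares the machine-value output with "model output using limit of detection and zero and a logistic regression using a detect/non-detect variable", and attaches a consequence: "If using a different approach for imputing IL-6 changes the results substantially, then our result is not easily interpretable".

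The same paragraph commits to reporting: "We will present the main effect results and associated statistics, including effect sizes and confidence intervals".

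Several things are not stated:
- what counts as a substantial change, and whether it is judged on the estimate, its direction, the interval or the p-value;
- whether one discordant analysis is enough;
- the LOD and the share of IL-6 values below it;
- the scale of the IL-6 model. Section 3.1 says "CRP observations were log transformed" but gives no transformation for IL-6.

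**The concern.** A sensitivity analysis is useful when it would agree with a correct primary result and disagree with a wrong one. These three comparators do not separate the two cases well.

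- **LOD substitution** puts every non-detect at the top of its possible range. Two values below the LOD become equal, so part of any real difference is lost.
- **Zero substitution** puts every non-detect at the bottom of its range. On the raw scale this usually widens the difference somewhat. If IL-6 is log transformed, as CRP is, it cannot be computed.
- **The detect/non-detect model** estimates an odds ratio for being above the LOD. Its coefficient cannot be compared in size with the linear one, and only people near the LOD inform it.

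So analyses that the SAP itself ranks as further from the truth can cast doubt on the one it prefers. With no definition of a substantial change, whether they do so is decided after the results are seen. At stake is the reading of one named secondary outcome.

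**Working it through.** The SAP gives no IL-6 power, effect size, LOD or non-detect share, so there is no planned figure to reproduce. The check asks how the comparators behave when the machine-value analysis is right.

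**Sample size.** Enrolled: 43 (Protocol section 3). Removed: 5 (SAP 4.2). Analysed: 43 − 5 = 38. SAP 4.1 counts 138 rumination questionnaires and refers to two time points per day, so 138 / 2 = 69 sessions. People with both sessions: 69 − 38 = 31. People with one: 38 − 31 = 7. This assumes the questionnaire count refers to the analysis set.

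**Expected shift under substitution.** Let X = log IL-6 at T4, normal with mean μ and SD σ. Let L = log LOD, p the non-detect share, z = Φ⁻¹(p) = (L − μ)/σ. For a small shift in μ, ignoring baseline adjustment, the ratio to the uncensored effect is:
- LOD, log scale: d E[max(X, L)]/dμ = P(X > L) = 1 − p. This gives 0.90, 0.70 and 0.50 at p = 10%, 30% and 50%.
- LOD, raw scale: Φ(σ − z). With σ = 0.75 (assumed) and p = 30%, z = −0.524 and Φ(1.274) = 0.90. With p = 50%, Φ(0.75) = 0.77.
- Zero, raw scale: Φ(σ − z) + φ(σ − z)/σ. At p = 30%: 0.899 + 0.177/0.75 = 1.14. At p = 50%: 0.773 + 0.301/0.75 = 1.17.

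**Simulation 1.** Assumptions: 31 pairs; lognormal IL-6 with log-SD about 0.71–0.79; true effects giving about 80% or 95% power on uncensored data; 5–70% non-detects; machine values equal to the truth plus 30% extra noise below the LOD; raw and log scales; 2,000 runs per setting. The linear model was approximated by the paired difference adjusted for the baseline difference, and the logistic model by McNemar's mid-p test.
- Median LOD / machine estimate: 0.92–0.99 at 5% non-detects, 0.59–0.87 at 30%, 0.37–0.70 at 50%, 0.19–0.49 at 70%.
- Median zero / machine estimate, raw scale: 0.98–1.19.
- Detect/non-detect power: 1–41% where uncensored power was about 80%, and 2–60% where it was about 95%.

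Share of true, significant machine-value results that would be flagged, by reading of the rule:

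| Reading of a substantial change | Share flagged |
|---|---|
| LOD or zero reverses the sign | 0–3% throughout |
| LOD or zero loses p<0.05 | 1–20% at up to 30% non-detects; 22–38% at 50%; 53–66% at 70% |
| LOD or zero estimate moves by more than 20% | 1–15% at 5% non-detects; 6–36% at 10%; 28–73% at 20%; 56–91% at 30%; 89–100% at 50% or more |
| Detect/non-detect must also reach p<0.05 | 54–98% at about 80% power; 37–98% at about 95% |

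**Simulation 2, with a censored mixed model added** (31 pairs, noisy machine values below the LOD, assumed variances).
- LOD, log scale: 0.84–0.91 of the machine estimate at 10% non-detects, 0.66–0.69 at 30%, 0.45–0.47 at 50%. These lie close to 1 − p.
- Zero, raw scale: 1.08–1.31.
- Detect/non-detect not significant in 48–92% of machine-significant trials.
- Left-censored random-intercept model: estimate 0.87–1.01 of the machine value. It lost p<0.05 in 2–34% of machine-significant trials, against 2–39% for LOD substitution.

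The last line matters for the fix. The censored model is much less biased, but at high non-detect shares it loses significance about as often as LOD substitution does. Keeping p<0.05 is therefore a poor test of agreement.

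**The case against.** A reader might infer that the rule would discard most true IL-6 effects. The documents do not support that, for four reasons.

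- The SAP's consequence is a caution about interpretation. Nothing is dropped, and effects and intervals are to be presented.
- The SAP sets no significance trigger. The highest flag rates come from requiring p<0.05 in the detect/non-detect model. The trigger sentence speaks of imputing IL-6, which that model does not do, so it may not count at all.
- For the two approaches that do impute, loss of significance flags more than half of true results only near 70% non-detects, and sign reversal almost never.
- The non-detect share is not given.

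It would also be too strong to say that zero and LOD substitution must move the estimate in opposite directions. Zero substitution gave a ratio as low as 0.98 in one simulated setting.

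A further defence is that placing non-detects at each end of their range shows how far the result depends on readings below the LOD. If both agree with the primary analysis, that is reassuring. The simulations also take the machine values as close to the truth, which is the very assumption such a check is meant to probe.

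All of this stands, and it limits the point. It does not remove it. A flag rate that runs from near 0% to 100% with the reading shows that the rule is not yet a rule. The shift under LOD substitution is predictable from the non-detect share alone, so seeing it says little about whether the machine values are sound.

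**Conclusion.** The point holds in limited form. With many non-detects, a correct machine-value result could often be labelled hard to interpret, because LOD substitution shrinks the estimate (to roughly 0.6–0.9 of its value at 30% non-detects), raw-scale zero substitution modestly inflates it, and detect/non-detect has far lower power at about 31 pairs. With 5% non-detects the substitutions change little. How often the label would apply cannot be stated, since neither the threshold nor the non-detect share is given.

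The sizes rest on assumed lognormal IL-6, assumed variances and effects, and machine values that are close to true. In Simulation 1 the paired and McNemar analyses approximate the SAP's models and leave out the 7 single-session participants. This is an inexpensive improvement to one secondary outcome and does not touch the primary outcome.

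**What to change.** Amend the IL-6 sentences of SAP 3.2 as follows.

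1. State the scale of the primary IL-6 model, the assay LOD and the share of values below it, by filter and time point.
2. Make one analysis bear on interpretability: a left-censored (Tobit) random-intercept model, censored at the LOD, with filter and baseline, on the same scale as the primary model. A detected value contributes its density. A non-detect contributes Φ((L − η)/σₑ), where η is the linear predictor including the random intercept, σₑ the residual SD, and L the LOD on the model's scale.
3. State how non-detect baselines enter. Using machine values, as in the primary model, keeps the two analyses different only in how the outcome is handled. Modelling baseline and T4 jointly as censored responses is the alternative.
4. Define agreement as the same direction and an estimate and 95% CI close to the machine-value result, with the margin written down in advance. Do not require that p<0.05 be kept. The simulated ratio of 0.87–1.01 suggests a margin wider than 13% (1 − 0.87).
5. Keep LOD and zero substitution as descriptive bounds, zero on the raw scale only, and detect/non-detect as supportive. None of these alone should make the result uninterpretable.

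The cost is a few sentences and a short program. No new data are needed, since Protocol section 3 says the assay software estimates the LOD. The downsides are a package other than lme4, a distributional assumption, and some loss of precision when about half the values are non-detects.
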